## Project Protocol

### Experimental design

The study consists of a mechanistic randomized placebo-controlled clinical trial with a mixed experimental design, whose objective is to assess which variables that have been linked to central sensitization (CS) in chronic pain patients can predict the response of chronic low back pain (CLBP) patients to spinal manipulative therapy (SMT). In order to do this, clinical, psychophysical and inflammatory variables will be measured in CLBP patients, which will be exposed to either SMT or a placebo SMT for 12 visits over a 4-week period. Another group made up of healthy volunteers will be used to determine the reference values of the same variables in a healthy population and compare them with the clinical population, before and after exposure. The primary outcome measures and main clinical variables are pain intensity and disability. All variables will be measured before the first SMT session, as well as at the end of the twelfth and last session, except for pain intensity, which will be measured at the start of each session for exploratory reasons.

**Figure 1.** Study protocol for the clinical trial

### Patient sample

For this study, participants will be recruited through the network of contacts of MCC and the Chiropractic Research Network. To be included in the study, patient participants must be of legal age (18-70 years old), receive a diagnosis of primary CLBP of at least 3-month duration, with or without leg pain (according to a clinical examination carried out at the Madrid College of Chiropractic – MCC). If pain affecting the low back or lower limb is suspected to be predominantly of neuropathic origin, the patient will be excluded (Kosek et al., 2021). Additionally, patients will be excluded from the study if they present any of the following criteria: evidence of specific pathology as the cause of their CLBP, diagnosis of mental illness or pain of equal or higher intensity affecting the hand / thumb or regions near the lumbar spine, use of corticosteroids, opiates or anti-cytokine medication, pregnancy, lumbar fusion surgery or recent laminectomy, having received SMT in the 12 months prior to the beginning of the study (Gerhardt et al., 2017; Klyne et al., 2019; Smart et al., 2012). The only exception to this will be patients with a diagnosis of anxiety and depression, as these conditions are very frequently comorbid with CLBP (Gore et al., 2012; Wong et al., 2021) and may also suggest a CS phenotype (Aoyagi et al., 2019; Smart, et al., 2012). Candidates interested in participating in the study will initially complete a questionnaire with the selection criteria, either in person at the MCC or online. If the criteria are met, patients will be scheduled an appointment where they will be provided with an information sheet so that they can read all the information in detail and ask any questions they see fit, before signing the informed consent. Subsequently, they will be referred for a clinical examination (consisting of a case history and physical examination) that will confirm the diagnosis of primary CLBP (see Figure 1–0).

## **Healthy population sample**

Additionally, a sample of healthy volunteers will be recruited to be used as a reference for the psychophysical and inflammatory variables collected in the sample of CLBP patients. The reference values obtained from this group will be compared to those of the patient population. To be included in the study, participants must be of legal age (18-70 years old), and present no current or chronic pain condition, as well as not having received any diagnosis of a systemic, inflammatory, neurological or psychiatric condition. They will age/sex matched to the patient group receiving SMT.

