In order to interpret the values obtained in patient groups, they will be compared with reference values obtained from the healthy controls to both CLBP groups. This will allow characterizing the patient groups to determine whether they show increased psychological symptoms, increased pain sensitivity and hyperalgesia as well as increased TNF-alpha levels compared with a reference healthy population. In order to do this, a series of mixed analyses of variance will be performed to examine differences in PPTs, urinary TNF- α levels, PCS, CSI, BDI-II and GAD scores before and after treatment between the three groups (control, SMT and placebo). To test a priori hypotheses, significant effects will be decomposed using planned comparisons. For the rest of the effects, Tukey's HSD will be used for testing any pair-wise comparisons between group means.

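### Diagnosed anxiety or depression is allowed in patients but not in healthy volunteers, so the patient–volunteer comparison of psychological scores is biased towards higher scores in patients, by an amount the documents do not allow us to fix

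*Protocol*

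**What the plan says.** **Patients** (Protocol, Patient sample). The exclusions include "diagnosis of mental illness or pain of equal or higher intensity affecting the hand / thumb or regions near the lumbar spine". One carve-out follows: "The only exception to this will be patients with a diagnosis of anxiety and depression, as these conditions are very frequently comorbid with CLBP". The protocol adds that these conditions may point to a central sensitization phenotype.

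**Volunteers** (Protocol, Healthy population sample). Entry requires no current or chronic pain and "not having received any diagnosis of a systemic, inflammatory, neurological or psychiatric condition". There is no carve-out for anxiety or depression. On matching, the section says only: "They will age/sex matched to the patient group receiving SMT".

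**Analysis** (SAP, Statistical analyses, last paragraph). Mixed analyses of variance compare PPTs, urinary TNF-α, PCS, CSI, BDI-II and GAD between control, SMT and placebo groups, before and after treatment. The purpose is to "determine whether they show increased psychological symptoms, increased pain sensitivity and hyperalgesia as well as increased TNF-alpha levels compared with a reference healthy population". Planned comparisons are used for a priori hypotheses and Tukey's HSD for other pairwise contrasts.

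The protocol's section on questionnaire variables describes BDI-II and GAD as the instruments for depression and anxiety symptoms. Neither document plans an adjustment, a restricted analysis or a caveat for the difference in entry criteria.

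**The concern.** BDI-II and GAD measure the very conditions that are screened out on one side and let in on the other. A person with diagnosed depression and back pain can enter as a patient. The same person without back pain cannot enter as a volunteer. Some of any difference in these scores therefore reflects who was allowed in. PCS and CSI are affected to the extent that they move with anxiety and depression. Matching on age and sex does nothing about this.

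What is at stake is one secondary conclusion, that patients with chronic low back pain (CLBP) carry more psychological symptoms than a healthy reference population. A reader could attribute to CLBP a difference partly supplied by the entry criteria.

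**Working it through.** The documents state no figure for this comparison: no prevalence, no score excess and no power calculation. There is nothing of the plan's own to reproduce, so the check is a simple model with declared assumptions.

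**Inputs**
- From the protocol (Sample size calculation): 50 patients per arm, 100 in total, and 50 volunteers.
- Assumed: *p*, the share of otherwise eligible pain-free people with diagnosed anxiety or depression; *q*, the share among enrolled patients; *k*, how much higher diagnosed people score, in SDs of the score within the diagnosed or undiagnosed class; *δ*, any effect of CLBP on the score beyond diagnosis.

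**Separating artefact from association.** Take the mean of undiagnosed pain-free people as 0.
- Patients as enrolled: *qk* + *δ*
- Volunteers as screened: 0
- Volunteers had the patients' exception applied to them: *pk*
- Planned contrast: *qk* + *δ*
- Contrast with equal criteria: (*q* − *p*)*k* + *δ*
- Artefact: the difference between these two contrasts, *pk*

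The artefact depends on the prevalence in pain-free people, not in patients. For example, with *p* = 0.10, *q* = 0.30, *k* = 1 and *δ* = 0, the planned contrast is 0.30 SD. Of this, 0.10 SD is artefact and 0.20 SD is a real association between CLBP and these diagnoses.

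**False-positive rate.** Suppose CLBP is unrelated to symptoms and diagnoses (*q* = *p*, *δ* = 0). The patient variance is 1 + *p*(1 − *p*)*k*² and the volunteer variance is 1. With *n* patients, SE = √[(1 + *p*(1 − *p*)*k*²)/*n* + 1/50], *z* = *pk*/SE, and the two-sided 5% rejection rate is Φ(*z* − 1.96) + Φ(−*z* − 1.96).

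Worked case, *p* = 0.10, *k* = 1.0: the patient variance is 1 + 0.09 = 1.09.
- 50 vs 50: SE = √(1.09/50 + 1/50) = 0.204, *z* = 0.10/0.204 = 0.49, rejection 0.078.
- 100 vs 50: SE = √(1.09/100 + 1/50) = 0.176, *z* = 0.57, rejection 0.088.

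| *p* | *k* | Artefact (SD) | 50 vs 50 | 100 vs 50 |
|---|---|---|---|---|
| 0.05 | 1.0 | 0.05 | 0.06 | 0.06 |
| 0.10 | 1.0 | 0.10 | 0.08 | 0.09 |
| 0.10 | 1.5 | 0.15 | 0.11 | 0.13 |
| 0.20 | 1.5 | 0.30 | 0.28 | 0.37 |
| 0.30 | 1.5 | 0.45 | 0.53 | 0.68 |
| 0.30 | 2.0 | 0.60 | 0.71 | 0.86 |

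With the same psychiatric criterion in both groups the artefact is 0 and the rate is 0.05.

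**Closer to the planned test.** The table uses a two-sample z test at one time point, whereas the SAP plans a three-group mixed analysis of variance. Simulating one time point with 50 per group at *p* = 0.30, *k* = 1.5, the omnibus F test rejects about 51% of the time and Tukey's HSD flags a given patient arm against controls about 34% of the time. At *p* = 0.10, *k* = 1.5, Tukey flags a given arm about 5% of the time. The rate thus depends on which SAP procedure applies; the shift in the mean does not.

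**The case against.** The strongest reply is that the contrast is descriptive. The SAP says "This will allow characterizing the patient groups to determine whether they show increased psychological symptoms, increased pain sensitivity and hyperalgesia"; it does not say that CLBP causes those symptoms. A healthy reference group is supposed to be healthy, and the patient exception has a stated reason, so each criterion is defensible alone. This stands, and it is why the planned comparison should be kept. It does not remove the point: the SAP draws a statement about patients from the contrast, and nothing tells the reader that the reference group was screened on what is being measured.

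A second reply is that the affected scales are peripheral. The protocol calls BDI-II and GAD exploratory and describes the volunteers mainly as a reference for psychophysical and inflammatory variables. That also stands and keeps the point secondary.

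A reader might infer more: that a significant difference would appear even if CLBP had no relation to psychological symptoms, at a false-positive rate above 50%, so that no conclusion is possible. The documents do not support this. Such rates need a prevalence of about 0.30 among pain-free people. The only relevant statement, "as these conditions are very frequently comorbid with CLBP", describes patients. At the low end of the assumed range the inflation is slight.

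A reader might also conclude that the whole statement should rest on undiagnosed patients. That could err in the other direction: if CLBP contributes to anxiety or depression, the restriction removes part of the genuine difference.

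**Conclusion.** The asymmetry is plain in the text and neither document corrects it. It biases the three-group comparison of BDI-II and GAD, and to a lesser degree PCS and CSI, towards higher scores in patients. The direction rests only on diagnosed people scoring higher on these scales. The size rests on two quantities the documents do not give: the prevalence of these diagnoses among otherwise eligible pain-free people and their score excess. It could be trivial (0.10 SD and 8–9% false positives at 0.10 and 1 SD) or substantial (0.45 SD at 0.30 and 1.5 SD, a prevalence without support in the documents). Any excess of diagnoses in patients beyond the pain-free prevalence is real association and should not be counted as artefact.

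The randomised SMT–placebo comparison, the two primary outcomes and the regressions within the SMT group do not use the volunteers and are unaffected. This is a cheap improvement to a secondary analysis.

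**What to change.** In the last paragraph of the SAP's Statistical analyses:

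1. Keep the planned all-patient comparison, and describe it as a contrast with a psychiatrically screened reference group.
2. Add a pre-specified comparison of BDI-II, GAD, PCS and CSI between patients without an anxiety or depression diagnosis and the volunteers. Adjust it for age and sex, because the restriction breaks the matching.
3. State that patients show increased psychological symptoms beyond the entry criteria only if the difference is also present in the restricted comparison.
4. Record an anxiety or depression diagnosis explicitly at screening. The selection questionnaire and case history should already yield it, but the protocol mentions comorbid chronic conditions only in general terms.

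The cost is some SAP wording, one recorded item and one further run of analyses already planned. The restricted comparison has fewer patients, possibly by a third if diagnoses are common, and it may understate the total difference if CLBP itself contributes to anxiety or depression. That is why both comparisons should be reported together.

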(Petrescu et al., 2010), and the average number of hours of sleep which may help predict pain patterns and will be used for exploratory purposes (Edwards et al., 2008). Additionally, the presence of any chronic conditions (including pain conditions) that is comorbid with the CLBP will be recorded for exploratory purposes.

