Official Title:

Efficacy of Chiropractic Spinal Manipulative Therapy in Patients With
Primary Chronic Low Back Pain: a Mechanistic Randomized Controlled
Trial

NCT number: Not Available

Unique Protocol ID: SMTCLBP

Date: December 15th, 2021

Statistical analyses

The normal distribution of the data will be verified using the Kolmogorov-Smirnov test. Data deviating from normality will be transformed to obtain a normal distribution before being entered into the data analysis. The two main outcome variables (clinical pain intensity and disability related to low back pain) will be compared between groups (SMT vs. placebo) over time (baseline and session 12) using a mixed analysis of variance. Average pain intensity since the previous treatment visit and in the seven days prior to the initial visit will be the variable used for statistical analyses. With an exploratory objective, the secondary variables (PCS, CSI, BDI-II, GAD scores, PPTs, degree of pain widespreadness, urinary cytokine levels, number and severity of reported adverse effects, presence of leg pain, pain medication use) will be compared between groups (SMT vs placebo) over time (baseline and session 12) using another mixed analysis of variance. To test a priori hypotheses, significant effects will be decomposed using planned comparisons. For the rest of the effects, Tukey's HSD will be used for testing any pair-wise comparisons between group means.

Pearson's product-moment correlation analyses will be carried out to examine the association between primary variables and secondary variables that demonstrate significant effects between groups over time. Subsequently, two multiple regression models will be used to examine the predictors of improvement in clinical pain and disability over time in patients who have received SMT, using secondary variables with a significant association with the primary variables. The secondary variables used for this analysis will be: baseline PCS and CSI score, baseline PPTs in the primary pain region, baseline TNF- α levels, and baseline expectations of pain relief. In addition, in another

regression model, the changes (delta) in these variables (except expectations of pain relief, since it is only measured at baseline) throughout the 4 weeks of treatment will be used as predictor variables. This is done to identify the variables most associated with clinical evolution, in order to answer the mechanistic question.

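### Volunteers with a systemic or inflammatory diagnosis are excluded but patients with one can enter, and the planned TNF-alpha comparison with volunteers ignores the comorbidity record

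*Protocol*

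**What the plan says.** **Volunteers.** Protocol, Healthy population sample: no current or chronic pain, and "not having received any diagnosis of a systemic, inflammatory, neurological or psychiatric condition". On matching: "They will age/sex matched to the patient group receiving SMT". No other matching factor is named.

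**Patients.** Protocol, Patient sample: disease other than mental illness or neuropathic pain excludes through "evidence of specific pathology as the cause of their CLBP". Medication excludes through "use of corticosteroids, opiates or anti-cytokine medication". Mental illness excludes, except anxiety and depression, which are admitted on purpose. No criterion covers systemic or inflammatory disease unrelated to the back pain.

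**Comorbidity record.** Protocol, Clinical examination variables: "the presence of any chronic conditions (including pain conditions) that is comorbid with the CLBP will be recorded for exploratory purposes". No analysis is attached to it.

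**Analysis.** The last paragraph of the SAP compares the control, SMT and placebo groups before and after treatment: "a series of mixed analyses of variance will be performed to examine differences in PPTs", with urinary TNF-alpha and the questionnaire scores in the same list. One stated purpose is to see whether patients show "increased TNF-alpha levels compared with a reference healthy population". No covariate, restriction or sensitivity analysis is named.

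**The concern.** Patient against volunteer is not a randomised contrast, so it is only as clean as the two sets of eligibility criteria make it. Here they differ on a factor that bears directly on the outcome. The protocol's sample size section describes TNF-alpha as a marker of inflammation in general. A disease that raises inflammation, and that can occur in only one of the compared groups, is a competing explanation for a raised level. Matching on age and sex does not remove it, because the exclusion applies to volunteers of every age and both sexes.

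At stake is how the finding is read. If patients have higher urinary TNF-alpha, readers may take that as a feature of chronic low back pain. The plan collects the information needed to probe this and then does not use it.

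**Working it through.** **Step 1: the criteria side by side.**

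| Feature | Volunteers | Patients |
|---|---|---|
| Systemic or inflammatory diagnosis | excluded | excluded only if it causes the back pain |
| Corticosteroids, opiates, anti-cytokine drugs | no criterion stated | excluded |
| Age and sex | matched to the SMT group | reference for matching |
| Chronic comorbidity | excluded as above | recorded, not analysed |

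The drug exclusions remove some treated inflammatory disease. Disease that is untreated, or treated with other drugs, stays eligible.

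**Step 2: where the comorbidity record is used.** It is absent from the SAP's list of secondary variables, its correlations, its regressions and its three-group analyses of variance.

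**Step 3: inputs for size.** Group sizes come from the protocol's sample size section: 5 predictors × 10 = 50 per patient arm, 2 × 50 = 100 patients, and 50 volunteers. The plan has no power calculation for the TNF-alpha comparison, so there is no figure of its own to reproduce. It also gives no comorbidity prevalence and no effect of comorbidity on TNF-alpha. Two assumptions are therefore needed: prevalence q from 10% to 30%, and effect D from 0.5 to 1.0 SD of (transformed) TNF-alpha.

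**Step 4: shift in the mean difference, shift = q × D.**
- Low: 0.10 × 0.5 = 0.05 SD
- Middle: 0.20 × 0.75 = 0.15 SD
- High: 0.30 × 1.0 = 0.30 SD

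**Step 5: what the shift does to a 5% two-sided test when back pain itself has no effect.** Standard error in SD units:
- one arm against volunteers: √(1/50 + 1/50) = 0.200
- both arms pooled: √(1/50 + 1/100) = 0.173

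The chance of significance, from the noncentral t distribution with 147 df (150 participants − 3 groups) and noncentrality shift/SE, is:

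| Shift (SD) | 50 v 50 | 100 v 50 |
|---|---|---|
| 0.05 | 5.7% | 5.9% |
| 0.15 | 11.6% | 13.8% |
| 0.30 | 32.0% | 40.6% |

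This is a simple two-group contrast at one time point, not the full mixed analysis. It also ignores the extra spread that a mixture of patients with and without comorbidity creates. Simulating that mixture lowers the top figures to 29.8% and 36.4%.

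**Step 6: cost of restriction.** Leaving out 30% of an arm of 50 leaves 35, and the standard error becomes √(1/50 + 1/35) = 0.220. For an assumed true difference of 0.5 SD, power falls from about 70% (50 v 50) to about 61% (50 v 35).

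**The case against.** The strongest reply is that the SAP does not claim back pain causes the increase. It speaks of characterising the patient groups against a healthy reference. For that descriptive question, a difference partly due to comorbidity is a true difference, and a reference group is meant to be healthy. This stands. The percentages in the working are error rates only if the result is attributed to back pain.

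Three further replies also stand in part. The size is wholly assumed, and at the low end the rate is barely above 5%. The protocol's comorbidity item names no systemic or inflammatory disease, so it shows that such patients can enter, not that many will. Urinary cytokines are a secondary variable, and the SAP labels the SMT-placebo analysis of those variables exploratory.

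A reader might infer more than the documents support:

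- *That TNF-alpha as a predictor of response is undermined in the same way.* It is not. The SAP's regressions concern patients who received SMT ("The secondary variables used for this analysis will be: baseline PCS and CSI score, baseline PPTs in the primary pain region", then TNF-alpha and expectations). Volunteers and their criteria play no part there. If comorbid inflammation raises TNF-alpha and TNF-alpha still predicts response, the prediction holds. The absence of a comorbidity term is an ordinary limitation of a prediction model, not a result of unequal criteria.
- *That agreement between the full and restricted analyses would justify attributing the difference to back pain.* It would not. The protocol itself links smoking to raised pro-inflammatory cytokines, and smoking is neither matched nor adjusted for. Nor does a loss of significance show confounding, since Step 6 shows that precision alone can cause it.
- *That the treatment comparison is affected.* SMT against placebo is randomised, and comorbidity should balance on average.

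**Conclusion.** The concern holds for the comparison of patients with volunteers on TNF-alpha, and only there. The criteria are unequal on systemic and inflammatory disease, and the comorbidity record is not used, so a raised level in patients could partly reflect other disease. Under the assumed prevalence and effect, the shift is 0.05 to 0.30 SD, which ranges from negligible to material. The documents cannot say where in that range the trial will fall. This is a minor point about interpreting a secondary comparison. It does not show that a raised TNF-alpha would be spurious.

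**What to change.** In the SAP paragraph on healthy controls:

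1. Add a pre-specified sensitivity analysis that repeats the patient-volunteer TNF-alpha comparison without patients whose comorbidity record shows a systemic or inflammatory diagnosis. Define beforehand which conditions count, and have them coded by someone blind to the TNF-alpha values.
2. Report both estimated differences with confidence intervals, and judge the sensitivity analysis by how far the estimate moves. Do not make the conclusion depend on both tests being significant.
3. Word the main result as patients as recruited against disease-free volunteers, and do not attribute it to back pain alone, whatever the restricted analysis shows.

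Restriction is cleaner than a comorbidity covariate, because volunteers by design have none of these conditions. It aligns the groups only on systemic and inflammatory diagnoses. The neurological and psychiatric parts of the volunteer criterion remain unmatched, and the admission of anxiety and depression is deliberate.

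The cost is SAP wording, a short coding list and lower precision in the restricted analysis. No new data, visits or eligibility changes are needed.

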### **Sample size calculation**

To determine the ideal number of participants, we have considered our first aim, which is to identify the variables linked to the CS phenotype that could help predict the response to treatment based on SMT for CLBP. In order to do this, we will perform a multiple regression analysis, using five independent variables as predictors, in particular the score on the pain catastrophizing scale (PCS) and central sensitization inventory (CSI) questionnaires (indicators of catastrophism and CS), the pressure pain thresholds (PPTs) in the primary pain area (marker of primary hyperalgesia), the urinary levels of the cytokine Tumor Necrosis Factor Alpha (TNF- $\alpha$ ; marker of inflammation) and finally the expectations of relief for each patient (indicative of potential placebo effects). The baseline values of these variables will be included in the multiple regression model. For each predictor variable, it is recommended to estimate about ten sample elements, therefore we predict that a sample size of 50 patients per group will be necessary (Ortega Calvo and Cayuela Dominguez, 2002). Taking into account two groups, one that will receive real SMT and the other placebo SMT, we will need a sample of 100 patients. An additional group of age and sex-matched healthy individuals without CLBP of the same size (50 participants) will be recruited to be used as a reference group, to determine

reference values in a healthy population for the predictor variables (questionnaires, PPTs, cytokines only)

Regarding the two main outcome variables (pain intensity and disability related to low back pain), we expect a reduction in pain and disability after one month in patients who receive 12 sessions of SMT compared to placebo. We aim to detect small to moderate effects since it is a one-month intervention in patients with chronic pain unresolved by other treatments over at least 3 months. Therefore, based on an effect size of  $f = 0.175$ , an alpha of 0.05, a power of 0.8 for 2 groups and 2 repeated measures (baseline and session 12), and a correlation between the repeated measures of 0.5, the size of the necessary sample is 34 patients per group and a total of 68 patients to detect statistically significant changes in clinical pain and disability. Therefore, our analysis based on the regression model to predict the clinical course provides us with a large enough size for both the first and second aims of this study.

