## **Independent variables**

A computer application (random-number generator) will be used to generate a randomization sequence and thus assign each patient to one of the two groups. The SMT group will receive 3 times a week for 4 weeks a session (total of 12) based on SMT of the most painful vertebral segment (see Figure 1–3). The SMT will be performed by a chiropractor with twenty years of experience in the techniques. They will be performed with the patient positioned in the lateral decubitus position, and applying a high-speed, low-amplitude force on each side of the manipulated segment, with the aim of generating at least one joint cavitation (perceptible sound). For this, the chiropractor will use a contact with the hypothenar surface or the last phalanx of the 2nd and / or 3rd fingers of the hand with the spinous process in question. In case of not perceiving a cavitation or joint movement, the SMT will be repeated once at the corresponding side. For the placebo group, the sham SMT will be performed with the patient in the same position in the lateral decubitus position, with the lower leg extended and the upper leg flexed, and an unintended force will be applied to the gluteal region (Chaibi, et al., 2015), also bilaterally (Figure 1–3). Any cavitation perceived during both real and placebo SMT will be recorded. Healthy volunteers will not receive any intervention during the same time frame of 4 weeks.

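### Healthy controls are matched on age and sex to the SMT arm, but the three-group analyses include neither factor, which costs precision

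*Protocol*

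**What the plan says.** The Protocol, under Healthy population sample, ties the matching to one arm: "They will age/sex matched to the patient group receiving SMT". Under Sample size calculation it says "An additional group of age and sex-matched healthy individuals without CLBP of the same size (50 participants) will be recruited", without naming an arm. The Experimental design section speaks of comparing the volunteers with the clinical population as a whole.

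The last part of the SAP's Statistical analyses, on interpreting the patient values, uses the volunteers against both arms: "they will be compared with reference values obtained from the healthy controls to both CLBP groups". The method is "a series of mixed analyses of variance will be performed to examine differences in PPTs, urinary TNF- α levels, PCS, CSI, BDI-II and GAD scores", over the control, SMT and placebo groups at both time points. No covariate, matched-pair term or restriction to the SMT arm is stated. Neither document says whether matching is individual or by frequency.

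Patients are randomised. Under Independent variables, the Protocol plans to "generate a randomization sequence and thus assign each patient to one of the two groups", and it mentions no stratification by age or sex.

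**The concern.** Matching on age and sex implies that the sponsor expects them to affect the reference variables: pressure pain thresholds, urinary TNF-α and the questionnaire scores. If so, a model that leaves them out keeps their variance in the error term. The placebo arm also has no directly matched reference group, so its age and sex balance with the controls depends on how the randomisation falls.

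The stake is limited. These comparisons decide whether the patients are described as having raised pain sensitivity, psychological symptoms and TNF-α relative to healthy people. They do not estimate the effect of SMT.

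**Working it through.** **The plan's own figures.** The group size is five predictors times ten: 5 × 10 = 50 ("therefore we predict that a sample size of 50 patients per group will be necessary"), and the healthy group is set equal to it. The separate calculation for pain and disability also reproduces. With f = 0.175, two measures, correlation 0.5 and alpha 0.05, the group-by-time noncentrality at N = 68 is 0.175² × 68 × 2 / (1 − 0.5) = 8.33. Power is 0.812 at N = 68 and just under 0.80 (0.7997) at N = 66, so 68 is the smallest equal-arm total. No power figure is given for the healthy-control comparison.

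**Inputs.** 50 per group is from the Protocol. R², the share of outcome variance explained by age and sex, is not in the documents; it is assumed at 0.05 to 0.30. The outcome SD is set to 1.

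**SMT against controls.** The unadjusted model reports a standard error of √(2/50) = 0.20. Under exact matching the true SD of the difference is √(2(1 − R²)/50): 0.190 at R² = 0.10 and 0.179 at R² = 0.20. The reported standard error is therefore too large and the test conservative.

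**Placebo against controls.** The mean difference in a covariate has SD √(2/50) = 0.20 covariate SD, with a 95% range of ±0.39. It moves the outcome contrast by up to 1.96 × 0.20 × √R², centred on zero. For sex, the 95% range is 1.96 × √(2p(1 − p)/50), which is ±20 percentage points at p = 0.5 and ±18 at p = 0.7 (p assumed).

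**Simulation.** 40,000 trials were simulated with one normal covariate, controls matched exactly to SMT, placebo randomised, one time point and a pooled three-group error. Power is at an assumed 0.5 SD difference. Arrows run from unadjusted to adjusted.

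| R² | SMT-control type I | SMT-control power | Placebo-control type I | Placebo-control power | 95% chance shift, placebo-control (SD) |
|---|---|---|---|---|---|
| 0.05 | 0.043 → 0.048 | 0.702 → 0.720 | 0.048 → 0.048 | 0.700 → 0.720 | ±0.088 |
| 0.10 | 0.039 → 0.050 | 0.714 → 0.748 | 0.052 → 0.052 | 0.703 → 0.744 | ±0.124 |
| 0.20 | 0.029 → 0.051 | 0.720 → 0.792 | 0.050 → 0.050 | 0.701 → 0.791 | ±0.175 |
| 0.30 | 0.020 → 0.050 | 0.735 → 0.847 | 0.051 → 0.051 | 0.703 → 0.841 | ±0.215 |

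Mean bias without adjustment was about zero for both contrasts.

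**Gain from adjustment.** The standard-error ratio is √(1 − R²): 0.949 at R² = 0.10 and 0.894 at R² = 0.20, a cut of 5% to 11%. This equals 1/0.90 = 1.11 to 1/0.80 = 1.25 times the participants. For placebo-control, the simulated SD of the estimate falls from 0.200 to 0.191 and 0.180 respectively, which agrees.

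**Where the gain applies.** Additive age and sex effects that are stable over four weeks cancel within a person. The gain is therefore in between-group tests; group-by-time tests gain little or nothing.

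**The case against.** The strongest reply is that the design already does the work. Matching balances age and sex between SMT and controls whether or not they enter the model. Controls matched to SMT also share the placebo arm's age and sex distribution in expectation, because placebo is randomised against SMT. The remaining imbalance is chance, which the ordinary standard error covers. There is also a rationale for favouring the SMT arm, since the SAP's regressions for predictors of improvement are fitted in SMT patients. All of this stands.

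Two stronger readings are therefore not supported.

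- A reader might infer that the matching is wasted. It is not: it removes age and sex confounding from the SMT-control comparison, and leaving the factors out of the model costs precision only.
- A reader might infer that the placebo-control comparison is biased or has an inflated false-positive rate. A 20-point sex imbalance, with an assumed sex effect of 0.5-0.8 SD, would shift the contrast by 0.10-0.16 SD (0.5-0.8 standard errors) and give a rejection rate of 8-13%. That rate is conditional on an imbalance near the 95% limit, which arises in about 4-6% of trials under those assumptions. Over all trials the rate is 0.049-0.052.

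The reply does not remove the case for adjustment. Readers will interpret one realised sample, and the unadjusted model neither corrects its imbalance nor recovers the precision that the matching makes available. Dropout could also disturb the balance at follow-up, though the documents give no basis for sizing this.

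**Conclusion.** The point holds as a minor loss of precision in a reference comparison. The texts are clear: controls are matched to SMT, compared with both patient arms, and analysed without age, sex or the matching. There is no systematic bias, and the unconditional type I error does not exceed about 5%; for SMT-control it is lower, 0.043 to 0.020 over R² of 0.05 to 0.30.

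If R² is 10-20%, adjustment would cut the standard error of between-group contrasts by about 5-11%. The size rests on that assumed R², on exact matching and on a single-covariate, single-time-point simplification.

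A reader might also infer that the trial's main result is at risk. It is not, because the healthy volunteers enter neither the SMT-placebo analysis of pain and disability nor the predictor regressions.

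**What to change.** In the SAP's three-group comparison with healthy controls, add age (continuous) and sex as covariates to every model. With 150 participants this takes the between-subject error degrees of freedom from 147 to 145. It should need no new data: age is an entry criterion for everyone, and both variables are needed for the matching. The one assumption is that sex is also recorded for placebo patients.

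State in the Protocol whether matching is individual or by frequency.

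Optionally, frequency-match the volunteers to all randomised patients. This would bring the Healthy population sample section into line with Experimental design, Sample size calculation and the SAP, and matching would no longer require knowledge of allocation. It is secondary and closer to a preference, because SMT-matched controls already match the placebo arm in expectation.
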